3.3.2 Rationale for Patient Population

Despite recent improvements in treatment options, the prognosis for patients with advanced NSCLC remains dismal, with a median OS in first-line therapy of approximately 12.5 months (Sandler et al. 2006). Platinum-based doublet chemotherapy is still the current standard of care, yet response rates have not improved beyond 20% (Schiller et al. 2002). These approved chemotherapies are associated with

significant toxicities (e.g., neuropathy, febrile neutropenia, myelosuppression, and alopecia) that negatively affect quality of life. Therefore, there is a continuing need for more efficacious, better-tolerated treatments.

Inhibition of PD-L1/PD-1 signaling has been shown to produce durable responses in a proportion of patients in several solid tumor types, including NSCLC (Topalian et al. 2012). However, the majority of first-line clinical data in NSCLC are from biomarker-selected populations, or limited to patients who have been treated in refractory second-line disease and beyond. Early data from nivolumab, a PD-1 inhibitor, have been reported in first-line NSCLC with a median OS of 22.6 months (Gettinger et al. 2015) and provide a strong rationale for evaluating atezolizumab as a first-line therapy in patients with Stage IIIB–IVB NSCLC.

3.3.3 Rationale for Allowing Patients to Continue Atezolizumab Treatment until Loss of Clinical Benefit

Conventional response criteria may not adequately assess the activity of immunotherapeutic agents because PD (by initial radiographic evaluation) does not necessarily reflect therapeutic failure (see Section 1.3). Because of the potential for pseudoprogression/tumor immune infiltration, this study will allow patients to continue to receive study drug after apparent radiographic progression, provided the benefit–risk ratio is judged to be favorable by the investigator in consultation with the patient. Therapy may continue beyond radiographic PD as determined by the investigator until they deem there is further loss of clinical benefit for the patient. Loss of clinical benefit is defined as unacceptable toxicity or symptomatic deterioration attributed to disease progression as determined by the investigator after an integrated assessment of radiographic data and clinical status.

3.3.4 Rationale for Collection of Blood Specimens

The primary biomarker objective of this study is to measure bTMB in to evaluate predictive cutoffs for a novel blood-based diagnostic assay. This may help predict which patients may benefit most from atezolizumab and may help future development of tissue-free diagnostic options for patients who have inadequate quality or insufficient quantity of tissue.

Blood samples will be collected at screening, baseline, during therapy, and at first evidence of radiographic disease progression or loss of clinical benefit in order to better understand the changes in bTMB and immune signature profiles and potential mechanisms of resistance upon progression. Blood samples will be collected at screening, on Day 1 of Cycles 1, 2, and 4 (mandatory), and on Day 1 of Cycle 3 (optional), to evaluate additional exploratory biomarker changes that may be associated with the therapeutic effects of atezolizumab or the pathogenesis of NSCLC (see [Appendix 2](#)). Methods for exploratory analysis include, but are not limited to, NGS, PCR, and proteomics-based approaches.

3.3.5 Rationale for Collection of Archival and/or Fresh Tumor Specimens

In this study, archival and/or fresh tumor specimens from each patient will not be mandated but will be strongly encouraged. Tissue biopsies (tissue blocks preferred) may be submitted at any time during the study, with biopsies from diagnosis (archival or fresh) and at progression preferred. For patients who provide tissue samples, NGS may be performed by Foundation Medicine. If performed by Foundation Medicine, the investigator can obtain results from these analyses in the form of an NGS report, which is available upon request directly from Foundation Medicine. The investigator may share and discuss the results with the patient, unless the patient chooses otherwise. The Foundation Medicine NGS assay, FoundationOne[®], has not been cleared or approved by health authorities. The NGS report is generated for research purposes and is not provided for the purpose of guiding future treatment decisions (see Section 4.5.7). Results may not be available for samples that do not meet testing criteria.

To assess mutational load in tissue (tissue tumor mutational burden [tTMB]), a mutational load algorithm will be applied to NGS data. Analysis will be retrospective.

In addition to the assessment of tTMB, other exploratory markers, such as those with potential predictive and prognostic value related to the clinical benefit of atezolizumab, tumor immunobiology, mechanisms of resistance, or tumor type, may also be analyzed. DNA and/or RNA extraction may be performed to enable NGS and PCR to identify somatic mutations to increase understanding of disease pathobiology.

3.3.6 Rationale for Biomarker Assessments

Despite the promising clinical efficacy of PD-L1/PD-L1 inhibitors in NSCLC, PD-L1 expression as determined by immunohistochemistry does not appear to identify all of the patients who derive clinical benefit from these drugs. Emerging evidence suggests that patients with a high burden of somatic mutations derive significant clinical benefit from anti-PD-1/PD-L1 therapy; thus, further development of mutation load as a predictive biomarker for atezolizumab is warranted.

Blood samples (mandatory) will be collected at baseline, during therapy, and at first evidence of radiographic disease progression or loss of clinical benefit. Tissue biopsies (tissue blocks preferred) may be submitted at any time during the study, with biopsies from diagnosis (archival or fresh) and at progression preferred. DNA and RNA extraction to enable analysis via NGS, expression, and/or PCR to identify somatic mutations that are predictive of response to study drug can increase the knowledge and understanding of disease biology. NGS techniques such as targeted sequencing may offer a unique opportunity to identify biomarkers of response. NGS may be performed by a clinical cancer genomic profiling laboratory (e.g., Foundation Medicine).

Genomics is increasingly informing researchers' understanding of disease pathobiology. Targeted NGS provides a multiplex characterization of the genome and, along with

clinical data collected in this study, may increase the opportunity for developing new therapeutic approaches. Data will be analyzed in the context of this study but will also be explored in aggregate with data from other studies. The availability of a larger dataset will assist in identification of important pathways, guiding the development of new targeted agents.

4. MATERIALS AND METHODS

4.1 PATIENTS

Approximately 150 patients with Stage IIIB–IVB, locally advanced or metastatic, EGFR/ALK–negative NSCLC who are immunotherapy-naive will be enrolled.

4.1.1 Inclusion Criteria

Patients must meet all of the following criteria to be eligible for study entry:

- Signed Informed Consent Form
- Age \geq 18 years
- ECOG performance status of 0 or 1
- Histologically or cytologically confirmed Stage IIIB–IVB NSCLC (based on the IASLC Lung Cancer Staging Project proposed for the eighth edition of the AJCC NSCLC staging see [Appendix 3](#))
 - Patients with histologically or cytologically confirmed Stage IIIB-IV NSCLC based on the seventh edition of the AJCC NSCLC staging system are also eligible for study entry.
- For patients who have received prior neo-adjuvant/adjuvant chemotherapy or chemoradiotherapy with curative intent for non-metastatic disease: a treatment-free interval of at least 6 months prior to enrollment.
- Patients with any PD-L1 test result by IHC are eligible for the study.
- Patients without a PD-L1 test result are eligible for the study.
- Measurable disease, as defined by RECIST v1.1 (based on the assessments detailed in Section [4.5.5](#)).
 - Previously irradiated lesions can only be considered measurable disease if disease progression has been unequivocally documented at that site since radiation and the previously irradiated lesion is not the only site of measurable disease
- Adequate hematologic and end-organ function, defined by the following laboratory test results obtained within 14 days prior to the first dose of study drug:
 - ANC \geq 1500 cells/ μ L without granulocyte colony-stimulating factor support
 - Lymphocyte count \geq 500 cells/ μ L
 - Platelet count \geq 100,000 cells/ μ L without transfusion
 - Hemoglobin \geq 9.0 g/dL

Patients may be transfused to meet this criterion.

- International normalized ratio (INR) or activated partial thromboplastin time (aPTT) $\leq 1.5 \times$ the upper limit of normal (ULN)

This applies only to patients who are not receiving therapeutic anticoagulation; patients receiving therapeutic anticoagulation must have an INR or aPTT within therapeutic limits for at least 1 week prior to enrollment.
- AST, ALT, and alkaline phosphatase $\leq 2.5 \times$ ULN with the following exceptions:

Patients with documented liver metastases: AST and/or ALT $\leq 5 \times$ ULN

Patients with documented liver or bone metastases: alkaline phosphatase $\leq 5 \times$ ULN
- Serum bilirubin $\leq 1.5 \times$ ULN

Patients with known Gilbert disease who have a serum bilirubin level $\leq 3 \times$ ULN may be enrolled.
- Calculated creatinine clearance ≥ 30 mL/min
- For women of childbearing potential: agreement to remain abstinent (refrain from heterosexual intercourse) or use a contraceptive method with a failure rate of $< 1\%$ per year during the treatment period and for at least 5 months after the last dose of atezolizumab.
 - A woman is considered to be of childbearing potential if she is postmenarcheal, has not reached a postmenopausal state (≥ 12 continuous months of amenorrhea with no identified cause other than menopause), and has not undergone surgical sterilization (removal of ovaries and/or uterus).
 - Examples of contraceptive methods with a failure rate of $< 1\%$ per year include bilateral tubal ligation, male sterilization, hormonal contraceptives that inhibit ovulation, hormone-releasing intrauterine devices, and copper intrauterine devices.
 - The reliability of sexual abstinence should be evaluated in relation to the duration of the clinical study and the preferred and usual lifestyle of the patient. Periodic abstinence (e.g., calendar, ovulation, symptothermal, or postovulation methods) and withdrawal are not acceptable methods of contraception.

4.1.2 Exclusion Criteria

Patients who meet any of the following criteria will be excluded from study entry.

- Prior treatment with immunotherapy for any stage NSCLC, including early-stage (neoadjuvant or adjuvant) disease.
- Patients with EGFR-sensitizing mutations and ALK rearrangements are excluded from the study and should be treated according to standard clinical guidelines. Refer to NCCN guidelines for recommendations on molecular testing (NCCN Guidelines 2016).

- Active CNS metastases requiring treatment as determined by computed tomography (CT) or magnetic resonance imaging (MRI) evaluation during screening and prior radiographic assessments
 - Patients with a history of treated asymptomatic CNS metastases are eligible, provided they meet all of the following criteria:
 - Only supratentorial and cerebellar metastases allowed (i.e., no metastases to midbrain, pons, medulla, or spinal cord)
 - No ongoing requirement for corticosteroids as therapy for CNS disease
 - No stereotactic radiation within 7 days or whole-brain radiation within 14 days prior to enrollment
 - No evidence of interim progression between the completion of CNS-directed therapy and the screening radiographic study
 - Patients with new asymptomatic CNS metastases detected at the screening scan must receive radiation therapy and/or surgery for CNS metastases. Following treatment, these patients may then be eligible without the need for an additional brain scan prior to enrollment, if all other criteria are met.
- Spinal cord compression not definitively treated with surgery and/or radiation, or previously diagnosed and treated spinal cord compression without evidence that disease has been clinically stable for ≥ 2 weeks prior to enrollment
- Leptomeningeal disease
- Uncontrolled tumor-related pain
 - Patients requiring pain medication must be on a stable regimen at study entry.
 - Symptomatic lesions amenable to palliative radiotherapy (e.g., bone metastases or metastases causing nerve impingement) should be treated prior to enrollment. Patients should be recovered from the effects of radiation. There is no required minimum recovery period.
 - Asymptomatic metastatic lesions whose further growth would likely cause functional deficits or intractable pain (e.g., epidural metastasis that is not currently associated with spinal cord compression) should be considered for loco-regional therapy if appropriate prior to enrollment.
- Uncontrolled pleural effusion, pericardial effusion, or ascites requiring recurrent drainage procedures (once monthly or more frequently)
 - Patients with indwelling catheters (e.g., PleurX[®]) are allowed.
- Uncontrolled or symptomatic hypercalcemia (>1.5 mmol/L ionized calcium or calcium >12 mg/dL or corrected serum calcium greater than ULN)
 - Patients who are receiving denosumab prior to enrollment must be willing and eligible to discontinue its use and replace it with a bisphosphonate instead while in the study.
- Malignancies other than NSCLC within 5 years prior to enrollment, with the exception of those with a negligible risk of metastasis or death (e.g., expected

5-year OS >90%) treated with an expected curative outcome (such as adequately treated carcinoma in situ of the cervix, basal- or squamous-cell skin cancer, localized prostate cancer treated surgically with curative intent, or ductal carcinoma in situ treated surgically with curative intent)

- Women who are pregnant, lactating, or intending to become pregnant during the study
 - Women who are not postmenopausal (≥ 12 months of non-therapy-induced amenorrhea) or surgically sterile must have a negative serum pregnancy test result within 14 days prior to initiation of study drug.
- History of severe allergic, anaphylactic, or other hypersensitivity reactions to chimeric or humanized antibodies or fusion proteins
- Known hypersensitivity to biopharmaceuticals produced in Chinese hamster ovary cells or any component of the atezolizumab formulation
- History of autoimmune disease, including but not limited to myasthenia gravis, myositis, autoimmune hepatitis, systemic lupus erythematosus, rheumatoid arthritis, inflammatory bowel disease, vascular thrombosis associated with antiphospholipid syndrome, Wegener's granulomatosis, Sjögren's syndrome, Guillain-Barré syndrome, multiple sclerosis, vasculitis, or glomerulonephritis (see [Appendix 7](#) for a more comprehensive list of autoimmune diseases)
 - Patients with a history of autoimmune-related hypothyroidism on a stable dose of thyroid-replacement hormone may be eligible for this study.
 - Patients with controlled Type 1 diabetes mellitus on a stable insulin regimen are eligible for this study.
 - Patients with eczema, psoriasis, lichen simplex chronicus, or vitiligo with dermatologic manifestations only (e.g., patients with psoriatic arthritis would be excluded) are permitted provided that they meet the following conditions:
 - Rash must cover <10% of body surface area
 - Disease is well controlled at baseline and only requiring low-potency topical steroids
 - No acute exacerbations of underlying condition within the last 12 months requiring treatment with either psoralen plus ultraviolet A radiation, methotrexate, retinoids, biologic agents, oral calcineurin inhibitors, or high-potency or oral steroids.
- History of idiopathic pulmonary fibrosis, organizing pneumonia (e.g., bronchiolitis obliterans), drug-induced pneumonitis, idiopathic pneumonitis, or evidence of active pneumonitis on screening chest CT scan
 - History of radiation pneumonitis in the radiation field (fibrosis) is permitted.
- Positive HIV test
- Active hepatitis B virus (HBV) infection (chronic or acute), defined as having a positive hepatitis B surface antigen (HBsAg) test at screening

- Patients with past or resolved HBV infection, defined as having a negative HBsAg test and a positive total hepatitis B core antibody (HBcAb) test, are eligible for the study. An HBV DNA test must be performed in these patients prior to enrollment.
- Active hepatitis C virus (HCV) infection, defined as having a positive HCV antibody test and a positive HCV RNA test at screening
- Active tuberculosis
- Severe infections within 4 weeks prior to enrollment, including but not limited to hospitalization for complications of infection, bacteremia, or severe pneumonia
- Significant cardiovascular disease, such as New York Heart Association cardiac disease (Class II or greater), myocardial infarction within 3 months prior to enrollment, unstable arrhythmias, or unstable angina
 - Patients with known coronary artery disease, congestive heart failure not meeting the above criteria, or left ventricular ejection fraction <50% must be on a stable medical regimen that is optimized in the opinion of the treating physician, in consultation with a cardiologist if appropriate.
- Major surgical procedure other than for diagnosis within 28 days prior to enrollment or anticipation of need for a major surgical procedure during the course of the study
- Prior allogeneic bone marrow transplantation or solid organ transplant
- Any other diseases, metabolic dysfunction, physical examination finding, or clinical laboratory finding giving reasonable suspicion of a disease or condition that contraindicates the use of an investigational drug or that may affect the interpretation of the results or render the patient at high risk from treatment complications
- Prior treatment with CD137 agonists or immune checkpoint blockade therapies, anti-PD-1, and anti-PD-L1 therapeutic antibodies
- Treatment with systemic immunostimulatory agents (including but not limited to interferons or interleukin 2) within 4 weeks or 5 half-lives of the drug, whichever is longer, prior to enrollment
- Any approved anti-cancer therapy or hormonal therapy within 3 weeks prior to enrollment; the following exceptions are allowed:
 - Hormone-replacement therapy or oral contraceptives
 - TKIs approved for treatment of NSCLC discontinued ≥ 7 days prior to enrollment; the baseline scan must be obtained after discontinuation of prior TKIs.
- Treatment with any other investigational agent or participation in another clinical study with therapeutic intent within 28 days prior to enrollment
- Received therapeutic oral or IV antibiotics within 2 weeks prior to enrollment
 - Patients receiving prophylactic antibiotics (e.g., for prevention of a urinary tract infection or to prevent chronic obstructive pulmonary disease exacerbation) are eligible.

- Administration of a live, attenuated vaccine within 4 weeks before enrollment or anticipation that such a live attenuated vaccine will be required during the study or for 5 months after the last dose of atezolizumab
 - Influenza vaccination should be given during influenza season only (approximately October to March).
 - Patients must not receive live, attenuated influenza vaccine (e.g., FluMist®) within 4 weeks prior to enrollment, at any time during the study, or for 5 months after the last dose of atezolizumab.
- Treatment with systemic corticosteroids or other systemic immunosuppressive medications (including but not limited to prednisone, dexamethasone, cyclophosphamide, azathioprine, methotrexate, thalidomide, and anti-tumor necrosis factor [TNF] agents) within 2 weeks prior to enrollment
 - Patients who have received acute, low-dose, systemic immunosuppressant medications (e.g., a one-time dose of dexamethasone for nausea) may be enrolled in the study after discussion with and approval by the Medical Monitor.
 - The use of inhaled corticosteroids for chronic obstructive pulmonary disease, mineralocorticoids (e.g., fludrocortisone) for patients with orthostatic hypotension, and low-dose supplemental corticosteroids for adrenocortical insufficiency are allowed.

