Because the response rate of single-agent atezolizumab in first-line treatment is unknown, we plan an interim futility analysis when 50% of enrolled patients have had at least 6 months of follow-up. At this interim analysis, the study will be stopped if ORR is likely to be 5% or less compared with an ORR of 15% or more. This reference endpoint is derived from preliminary evidence with nivolumab as first-line monotherapy in NSCLC in which ORR ranged from 15% to 26% depending on histology (Gettinger et al. 2015). Additionally, historical response rates for standard-of-care platinum-doublet chemotherapy are roughly 15% to 20% (Schiller et al. 2002).

Study ML39237 will enroll patients who are naive to immunotherapy and for whom atezolizumab can represent a reasonable benefit–risk option. Patients whose tumors

are known to harbor sensitizing EGFR mutations or ALK rearrangements should be treated with appropriate targeted agents such as an EGFR tyrosine kinase or ALK inhibitor, respectively (see specific exclusion criteria in Section 4.1.2), and should not be enrolled in the study. Patients are eligible for study regardless of PD-L1 status, even if the status is unknown (see specific inclusion criteria in Section 4.1.1).

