2. OBJECTIVES AND ENDPOINTS

The aim of this study is to evaluate the clinical efficacy of atezolizumab as a single-agent, first-line therapy in patients with immunotherapy-naïve, Stage IIIB–IVB NSCLC. Diagnostic selection of patients will not be a criterion for enrollment.

The primary biomarker objective is to measure tumor mutational burden from blood (bTMB) and to evaluate whether it can predict for improved clinical outcomes with atezolizumab. Clinical outcome, as measured by PFS, will be correlated to bTMB retrospectively to define the threshold for positivity. Specific objectives and corresponding endpoints for the study are outlined in [Table 3](#).

Table 3 Objectives and Corresponding Endpoints

Objectives	Corresponding Endpoints
Primary Efficacy Objective:	

 To evaluate the clinical efficacy of atezolizumab 	
 INV-assessed ORR by RECIST v1.1
Secondary Efficacy Objective:	

 To evaluate the efficacy of atezolizumab 	
 INV-assessed ORR by RECIST v1.1 INV-assessed PFS by RECIST v1.1 INV-assessed duration of response by RECIST v1.1 Overall survival
Safety Objective:	

 To evaluate the safety and tolerability of atezolizumab 	
 Incidence of adverse events, with severity determined through use of NCI CTCAE v4.0
Primary Biomarker Objective:	

 To evaluate whether “positive vs. negative bTMB” defined at various bTMB quantiles can predict for improved PFS with atezolizumab 	
 Relationship between INV-assessed PFS and various bTMB quantiles
Secondary Biomarker Objectives	

 To evaluate the correlation between clinical outcomes including but not limited to PFS, PFS rate at 6, 9, and 12 months, ORR, and various definitions of positive bTMB 	
 Relationship between efficacy endpoints including INV-assessed PFS rate at 6, 9, and 12 months, ORR and various bTMB quantiles and efficacy
Exploratory Biomarker Objectives in Blood:	

 To evaluate whether higher expression of an immune-related gene signature in blood PBMCs predicts for improved PFS with atezolizumab 	
 Relationship between PFS and expression of an immune gene signature in PBMCs

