4.2 METHOD OF TREATMENT ASSIGNMENT AND BLINDING

This is an open-label single-arm study. Patients who meet all of the inclusion criteria and none of the exclusion criteria as assessed during the screening period will be enrolled in the study to receive treatment with atezolizumab.

The screening tests and evaluations will be performed within 28 days prior to Cycle 1, Day 1. Results of standard-of-care tests or examinations performed prior to obtaining informed consent and within 28 days prior to Cycle 1, Day 1 may be used; such tests do not need to be repeated for screening.

After written informed consent has been obtained and eligibility has been established, the study site will obtain the patient's unique identification number by registering the patient in an interactive voice/Web response system (IxRS) on the day of enrollment.

Patients should receive their first dose of study drug on the day of enrollment if possible. If this is not possible, the first dose should occur within 5 business days after the patient is registered in the IxRS.

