9.2 PROTOCOL DEVIATIONS

The investigator should document and explain any protocol deviations. The investigator should promptly report any deviations that might have an impact on patient safety and data integrity to the Sponsor and to the IRB/EC in accordance with established IRB/EC policies and procedures. The Sponsor will review all protocol deviations and assess whether any represent a serious breach of Good Clinical Practice guidelines and require reporting to health authorities. As per the Sponsor's standard operating procedures, prospective requests to deviate from the protocol, including requests to waive protocol eligibility criteria, are not allowed.

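### Does the first-line aim need a stated bar on earlier systemic therapy, or a committed efficacy analysis split by it?

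*Protocol*

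**What the plan says.** Protocol Section 2 gives the aim as to "evaluate the clinical efficacy of atezolizumab as a single-agent, first-line therapy in patients with" immunotherapy-naive Stage IIIB–IVB disease. Section 1.3 builds the interim look on the same setting: "Because the response rate of single-agent atezolizumab in first-line treatment is unknown, we plan an interim futility analysis".

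The criteria that touch earlier treatment are these:

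- Section 4.1.1 requires "a treatment-free interval of at least 6 months prior to enrollment", but only after curative-intent chemotherapy or chemoradiotherapy for non-metastatic disease.
- Section 4.1.2 bars prior immunotherapy, checkpoint inhibitors and CD137 agonists outright.
- For other treatment, Section 4.1.2 sets a window: "Any approved anti-cancer therapy or hormonal therapy within 3 weeks prior to enrollment; the following exceptions are allowed". One exception is "TKIs approved for treatment of NSCLC discontinued" at least 7 days before enrolment. Investigational agents have a 28-day window.
- Section 4.1.2 also says "Patients with EGFR-sensitizing mutations and ALK rearrangements are excluded from the study".

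Entry follows these lists: "Patients who meet all of the inclusion criteria and none of the exclusion criteria as assessed during the screening period will be enrolled" (Section 4.2).

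On analysis, Protocol 6.4 and SAP 4.2 take all patients who received a dose. SAP 4.3 gives an open-ended list of baseline characteristics that includes metastatic lung cancer history and prior radiotherapy but does not name prior systemic therapy. SAP 4.6.5 commits to a summary of previous medications and other anti-cancer treatment. Protocol 6.4.3 and SAP 4.5.3 allow efficacy to be explored by baseline characteristics, without requiring it and without naming prior therapy.

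**The concern.** In a single-arm study the ORR is read against outside experience, so it matters who was treated. The label is first-line, yet none of the criteria in Sections 4.1.1 and 4.1.2 or the synopsis excludes someone given chemotherapy for metastatic disease and stopped more than 3 weeks before entry. The authors wrote outright bars where they wanted them, as for immunotherapy, and the tyrosine kinase inhibitor (TKI) exception presupposes that some earlier lung cancer treatment is admissible.

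If such patients entered, the all-treated ORR, progression-free survival (PFS) and overall survival (OS) would mix lines of therapy. The plan does not promise to show the result without them, so the choice to show it could be made after the data were seen. At stake is whether the first-line label fits the reported estimates.

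**Working it through.** **Do the criteria leave the gap?** Yes. Apart from the outright bars on immunotherapy-type agents, Section 4.1.2 limits prior drug treatment by time, and Section 4.4.3 also speaks only of time periods. The 6-month interval in Section 4.1.1 does not reach treatment of advanced disease. The TKI route is probably narrow because EGFR- and ALK-positive disease is excluded. Figure 1 is not reproduced in the text available, so any entry there cannot be checked.

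**The plan's own figures first.**

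- Maximum 95% half-width at n = 150: 1.96 × √(0.25/150) = 8.0 points, as stated in Protocol 6.1.
- Futility rule of 4 or fewer responses in 75: P(X ≤ 4) is 67.9% at ORR 5% and 0.84% at ORR 15%. These match the stated figures of above 67% and below 1% in Protocol 6.7.1.

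**Inputs for the size of the effect.** Protocol 1.2.2.2 reports, from one earlier atezolizumab study, an ORR of 19% in 139 chemotherapy-naive patients and 17% in 520 pretreated patients, all PD-L1-selected. The pretreated share w in the present study is not given; 10, 20 and 30% are assumed.

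**Pooled ORR** = (1 − w) × 19% + w × 17%. The last column is P(X ≤ 4) for 75 patients at that ORR.

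| w | Patients of 150 | Pooled ORR | Shift (points) | Futility stop |
|---|---|---|---|---|
| 0 | 0 | 19.0% | 0 | 0.065% |
| 10% | 15 | 18.8% | 0.2 | 0.074% |
| 20% | 30 | 18.6% | 0.4 | 0.085% |
| 30% | 45 | 18.4% | 0.6 | 0.097% |

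**Precision for comparison.** The Blaker 95% interval for 28/150 is about 12.9 to 25.6%, a half-width of about 6.3 points.

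**Uncertainty in the 2-point contrast.** SE = √(0.19 × 0.81/139 + 0.17 × 0.83/520) = 0.0371. The 95% interval is 2 ± 1.96 × 3.71 = −5.3 to 9.3 points. Multiplied by w = 0.3, the pooled ORR could lie from 2.8 points below to 1.6 points above the first-line ORR. At the lower edge, 19 − 2.8 = 16.2%, the futility stop probability is 0.40%.

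**Other starting points.** Protocol 1.3 quotes a first-line range of 15 to 26% for another drug.

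- From 26%, with 17% in pretreated patients, w = 0.3 gives 0.7 × 26 + 0.3 × 17 = 23.3%, a shift of 2.7 points.
- From 15%, with the same 2-point deficit (13% in pretreated patients), w = 0.2 gives 14.6% and w = 0.3 gives 14.4%. The futility stop probability becomes 1.06% and 1.20%, against 0.84% at 15%.

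**What a split would give.** At an ORR near 19%, the Blaker half-width in the subset without prior therapy is 6.9 points at n = 135 and 7.7 points at n = 105, wider than the all-treated interval.

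**The case for a change.** The strongest reply is that a small expected shift does not verify the label. The 19% and 17% come from a PD-L1-selected study, the contrast is imprecise, and its interval reflects sampling error only; it does not bound the difference in this unselected population. Prior cancer therapies are collected (Protocol 4.5.2), so a baseline row and a conditional supplementary analysis would be cheap, and committing to them now would remove later discretion. The sponsor also protects another population attribute: SAP Section 3 continues recruitment until 150 EGFR- and ALK-negative patients are enrolled.

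Part of this stands. The gap in the criteria is real, and the commitment in SAP 4.6.5 describes treatment history without separating efficacy by it. The claim that the futility risk stays below 1% also depends on the starting ORR, as the 15% case shows.

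The rest carries less weight. The rule that deviation requests, "including requests to waive protocol eligibility criteria, are not allowed" (Section 9.2), keeps ineligible patients out; it does not oblige a site to enrol someone outside the stated first-line design. It is not established that the split needs no new data: Section 4.5.2 and the schedule of activities list prior therapies, stage and diagnosis date, but do not show that treatment setting is recorded for each regimen, which is needed to tell advanced-disease therapy from adjuvant therapy. Naming one baseline row and making one permitted subgroup mandatory adds detail that an analyst would supply anyway if the summary of previous treatment showed such patients.

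**Conclusion.** No change to the plan follows. The aim and the criteria do not match word for word, and this is best read as a drafting gap: first-line intent is stated in the aim, the design description and the interim rationale, and the documents do not show that pretreated patients were intended or enrolled. If any were, the committed summary in SAP 4.6.5 should bring them to light, and SAP 4.5.3 already permits efficacy to be described by subgroup.

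At assumed pretreated shares of 10 to 30% the expected ORR shift is 0.2 to 0.6 points. It is up to 2.8 points at the edge of the sampling interval, or 2.7 points from a 26% base. All are inside the 6.3-point half-width expected at 28/150 and the 8-point maximum that the design accepts. The futility stop probability is at most 0.40% from a 19% base and 1.20% from a 15% base, so the interim decision is practically unaffected.

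These figures rest on assumed shares and on a contrast from a PD-L1-selected study. They say nothing about PFS or OS, for which no shift is shown. Stating the first-line requirement in the criteria would be tidier, but it would change who is treated only if enrolment were still open, which the documents do not say.
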